6. INTERVENTION

A. Informed Consent

Prior to any intervention required for CAST that is not part of usual care required for the patient, appropriate informed consent will be obtained. The informed consent must have prior Institutional Review Board approval.

B. Enrollment

It is the intention of the study that there should not be interventions which affect arrhythmia, other than the study drugs, between the qualifying Holter and the end of the study. It is required that there be no non-study interventions planned or being considered which might affect arrhythmia between the qualifying Holter and completion of the study drug titration.

Since it is expected that 2 to 5 days, excluding weekends, will elapse between the qualifying Holter and the beginning of study therapy, and since titration will require between about 10 - 60 days (see below), a patient should not be screened unless it seems likely that there will be no inappropriate interventions for at least 30 days.

If a patient's situation meets the conditions listed above, the investigator will obtain an informed consent for the purpose of administering the screening Holter (unless part of standard care) and for inclusion of the patient identifying information into the Holter registry. (The latter may be delayed for patients who qualify for CAST until after they have been approached for participation in CAST).

If the qualifying Holter meets the CAST enrollment criteria as read locally, then informed consent will be obtained for the titration and randomized phases of the study. All qualifying Holter tapes must be kept at the center for the duration of the study.

A radionuclide ventriculographic, angiographic or M-mode or 2D echocardiographic ejection fraction must be obtained prior to randomization at least 24 hours post MI. A separate consent form may be necessary for this procedure. Suggested timing of these tests is given in Table 6.1. Titration must be completed and blinded therapy instituted within 90 days of the qualifying Holter.

Table 6.1 Recommended Timing of Tests

Qualifying Holter	Day 0	Must be (≥Day 6 and < 2 years from MI)
Scanning of Qualifying Holter for Eligibility	Day 1	
Global Ejection Fraction (if not already available)	Day 1 or 2	(≥Day 1 from MI)
Informed Consent and Baseline data collection	Day 1 to 3	(≥Day 6 from MI)
Assignment to titration sequence	Day 2 to 4	(≥Day 6 from MI)
Start of Titration	Day 3 to 64	(≥Day 6 from MI)
Blinded Therapy	Day 8 to 89	(<Day 90 from Day of qualifying Holter)

Assignment to titration sequence will be by telephone call to the Coordinating Center, during which acknowledgment of informed consent, dates of the various tests and test results needed to qualify and stratify will be required.

Between the informed consent for titration and beginning titration, collection of the baseline data must be completed. To assure completion of titration within 90 days of the qualifying Holter it will usually be necessary to start titration within 2 to 3 weeks.

C. Titration Schedule

Titration will be completed within 90 days of the day when the qualifying Holter was obtained. In order to achieve blood level plateaus a minimum of four half-lives must elapse between initiation of a particular drug and dose and evaluation of that drug and dose. There must be a minimum of two days washout between drugs. Based on the experience in CAPS, it is anticipated that 50% of the patients will achieve suppression on the low dose of the first drug.

However, perhaps 10 to 15% of the patients will be evaluated at every dose of each drug. Thus, assiduous attention to titration will be necessary to assure timely completion.

For convenience of scheduling, it is recommended that remonitoring should be scheduled on or after day 4 but no later than day 10. Evaluation should be completed in the next 1 to 2 days. Thus, a complete cycle could require as few as 5 days or as many as 12 days.

D. Drug Sequences

The drug sequences are shown below. All sequences for which a patient is eligible will have equal probability of being assigned. Titration must proceed in the sequence shown.

Titration Sequences

$EF \geq 0.30$

A low -> A high -> B low -> B high -> C low -> C high
C low -> C high -> B low -> B high -> A low -> A high

where, at least initially, A = encainide, B = moricizine and C = flecainide.

$EF < 0.30$

D low -> D high -> E low -> E high
E low -> E high -> D low -> D high

where, at least initially, D = encainide and E = moricizine.

E. Criteria for Suppression

Suppression will be defined as $\geq 80\%$ reduction in VPD's/hr and $\geq 90\%$ reduction in runs/hr as compared to baseline (minimum of 18 analyzable hours) and without the presence of intolerable adverse effects (defined below).

F. Criteria for Selecting Drug and Dose.

A Holter is required at each drug and each dose evaluation unless adverse effects are noted, including an ECG exclusion noted on an arrhythmia monitor. ECG intervals throughout dosing will be measured and documented via a Holter rhythm strip. Submission of Holter data is required to document suppression as defined above or at least minimal suppression on the best drug and dose when 80% suppression is not obtained. When a Holter is obtained that does document suppression, as defined above, titration is to cease at that point, and the drug and dose the patient is suppressed on will be the designated drug and dose for that patient. The Holter tape documenting suppression or best drug and dose (in addition to the qualifying Holter) must be kept at the center until the end of the study.

G. Conditions Requiring Specific Actions during Titration.

1. Conditions requiring permanent cessation of titration. (This patient would not be randomized to blinded therapy and would not be followed as a patient in the main CAST study.)

a. The appearance of any entry exclusion criteria proven by washout not to be due to drug toxicity with the exceptions explained and described below:

Certain of the exclusion criteria were included because they were thought to yield a high probability that with the addition of active CAST therapy a safety concern would emerge. However, once a patient has agreed to participate and even entered titration there is no reason to exclude the patient unless the limit for concern is achieved. For this reason criteria 19, 21, and 22 are modified to:

QRS \geq 0.20 seconds

QTc \geq 0.6

Any pause of \geq 3.5 seconds

b. Resuscitated cardiac arrest when not clearly attributable to the drug.

2. Events requiring interruption of titration

Events such as open heart surgery, angioplasty, valve replacement, recurrent myocardial infarction, non-cardiac surgery and aneurysmectomy will require interruption of titration.

If, in the judgment of the investigator, the patient's VPD rates and EF are not significantly altered, the titration may be resumed, where discontinued, at least one week following the event.

If the investigator judges it prudent to obtain new baseline Holter and LVEF, the patient can restart titration. However, any drug for which an adverse effect not alterable by the event had already been demonstrated will be eliminated during the retitration, as will flecainide if the latest LVEF is $<$ 0.30.

Digitalis, beta blockers, beta agonists, phenothiazines, tricyclic antidepressants, theophylline derivatives, calcium channel blockers, and anticonvulsants might have some effect upon the incidence of ventricular arrhythmias, but the effect is not likely to be a major one. Every effort should be made to maintain constant therapy during titration but changes in the above drugs will not require special procedures or changes in the titration process.

3. Conditions Shown to Be Due to the Drug Requiring Proceeding to the Next Drug in the Sequence.

- a. Arrhythmias producing symptoms. Only serious symptoms such as syncope or presyncope should be considered under this criterion. Palpitations alone would not be regarded as a toxic endpoint.
- b. Sustained ventricular arrhythmias, torsades de pointes or a run of ≥ 15 consecutive VPD's at a rate of $\geq 120/\text{min}$.
- c. Any significant increase in the VPD rate or any significant increase in runs. A significant increase in VPD's includes proarrhythmia, ≥ 1500 VPD's/hr, or other significant increase.

For those patients showing ≥ 5 runs/day on the baseline Holter, a ten-fold increase will be considered a toxic endpoint. For patients with fewer than 5 runs/day on baseline, 50 or more runs will be considered toxicity.

- d. Prolongation of the QTc interval ≥ 1.4 times baseline and/or ≥ 0.6 sec. The rationale for this criterion is based upon the observation that patients showing marked lengthening of the QTc interval in response to antiarrhythmic agents (usually type I agents) seem to be at increased risk of syncope or sudden death.
- e. Development of the following abnormalities in impulse formation or conduction:
 - heart rate < 30 for a period lasting a minimum of 1 minute.
 - any pause ≥ 3.5 seconds.
 - second degree Mobitz type II A-V block.
 - advanced or third degree A-V block.
 - QRS width ≥ 2 times baseline or ≥ 0.20 sec.
- f. Resuscitated cardiac arrest. The patient may proceed to the next CAST drug in the sequence if evidence suggests that the episode is almost certainly due to the drug. However, the investigator can choose to end titration if he does not want to continue through the CAST drug sequence.
- g. Development of new or worsened CHF symptoms which are not controlled by therapy for the CHF and which after washout (of sufficient duration for the drug to be eliminated and the physiology to return to normal) are judged by the investigator to be due to the drug.
- h. Intolerable adverse symptoms.

- i. Investigator concern about safety based on evaluation on dose 1.
(Note however, titration does not permit return to a previous drug
in the sequence.)

H. Washout Procedure

Washout during titration to verify possible toxic adverse effects or proarrhythmia is to be a minimum of 4 half-lives. Verification is optional; however, return to a previous drug in the sequence is not permitted during titration.

I. Initiation of Blinded Therapy

Patients whose ectopy was successfully suppressed during titration will be randomly assigned to the successful therapy or to matching placebo. Therapy will be instituted immediately in an outpatient setting.

Patients whose ectopy was not successfully suppressed will not be eligible for the main study, but will be randomized to the best CAST therapy or a matching placebo and followed in the same manner as the main study patients. The best CAST therapy will be defined as that which is tolerated and is most effective.

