19. QRS \geq 0.18 seconds noted \geq 6 days after the onset of MI.
20. * WPW syndrome.
21. * Congenital long QT syndrome.
22. Prolonged pause of \geq 2.5 seconds noted \geq 6 days after the onset of MI.
23. Mobitz II 2nd degree, advanced or 3rd degree AV block noted \geq 6 days after the onset of MI.
24. Symptomatic sinus node dysfunction.
25. Heart rate $<$ 30 beats per minute for a period lasting at least one minute noted \geq 6 days after the onset of MI.

Drug Therapy

26. Previous serious adverse effect from drug(s) used in CAST.
27. On concurrent antiarrhythmic drug therapy, excluding digitalis, beta blockers, and calcium channel blockers.
28. Any intravenous or oral amiodarone within the last 2 weeks.
29. Any oral amiodarone within the last 6 months.
30. Intravenous amiodarone for \geq 48 hours within last 6 months.

Holter Findings

31. Symptomatic (hemodynamically important) unsustained VT or VT \geq 15 consecutive complexes at a rate \geq 120 beats per minute (disqualifying VT) noted \geq 6 days after the onset of the myocardial infarction (noted on Holter).
32. Insufficient arrhythmia ($<$ 6 VPD's/hr) on both screening Holters.

Miscellaneous

33. Psychologically or physically unfit to participate in the study.
34. Patient is geographically inaccessible.
35. Interpretation of Holter technically difficult.
36. Patient enrolled in a competing interventional trial, e.g., undergoing blinded therapy. Participation in followup after intervention is completed (e.g. thrombolytic trials) may be permissible and will be decided by the Executive Committee on a study by study basis.

C. Recruitment/Screening

Screening Log

Centers will be required to maintain a screening log for all patients identified who are age and CAST MI eligible patients. This log will include minimal information: name, age, sex, date of CAST MI, and principal reason for exclusion when applicable. Data entry will include a log number but not the name.

Holter Registry

A registry will be maintained for all consenting patients who are medically eligible, i.e., are not excluded by any of the *'d exclusions. Patient identifying information, consisting of name, date of birth, social security or other identifying number, and sex will be obtained together with the Holter findings and EF if available (see Appendix 4).

D. Stratification for Randomization

Stratification for randomization will be done on the following variables:

1. Clinical center
2. Left ventricular ejection fraction.

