7. RANDOMIZATION

A. Methods

Titration sequencing will be accomplished by telephone communication with the Coordinating Center. At the time of the call, the center calling will be required to provide data needed for stratification, assurance that no exclusionary criteria are present and that the informed consent was signed, and the patient identification number. The center will be provided with a titration sequence. The telephone communication will be made in one of two ways.

1. On working days, between the hours of 7:00 am and 5:00 pm Pacific Time, a call must be placed to a person at the Coordinating Center.
2. At other times, the communication will be by terminal access with the Coordinating Center computer. In this case, the computer will collect the data and assign the therapy sequence. On the first working day following the computer call, the Coordinating Center will review the data.

A second call will be required to complete the randomization process, after the titration sequence has been completed. The blinded therapy assignment that the patient will be followed on for the duration of the study will be given to the center at that time.

B. Titration Sequence

At the time of the initial call the titration sequence will be assigned. The titration sequence list will have been established previously, using blocking factor(s) known only to the Coordinating Center and based on the primary stratification factors of clinical center, ejection fraction and time from MI. These lists will be generated so that each titration sequence will have equal opportunity of exposure. Should drugs be eliminated or added following study start up, the lists will be regenerated to maintain this rationale.

C. Blinded Therapy

Following titration, blinded therapy will be assigned at the completion of a second randomization call to the Coordinating Center.

At the time of this call the Coordinating Center will do the following:

For main study patients:

Require the baseline VPD and run rates and the evaluation VPD and run rates, in order to check the computation showing suppression, as well as the drug and dose of successful therapy. Assign therapy taken from pregenerated lists based on blocking factor(s) known only to the Coordinating Center and based on the stratifying factors of clinical center, ejection fraction and time from MI, as well as on the successful therapy.

For unsuppressed patients:

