qualify on the first 24 hour Holter, a second Holter may be performed within the entry window. Failure to qualify on two screening Holters excludes the patient from further consideration for the study for that MI. A rhythm strip for interval measurements is to be made for each Holter and retained in the patient files. The qualifying and suppression Holter tapes must be retained indefinitely.

Baseline Measures

1. Measure of LV function

A baseline measurement of left ventricular ejection fraction will be required prior to randomization. This measurement must be obtained ≥ 24 hours after the qualifying MI and within 90 days of the qualifying Holter (the 90 day rule is removed if the EF is < 0.30). The ejection fraction may be determined by:

- a. Radionuclide ventriculography
- b. Left ventricular contrast angiography
- c. Digital subtraction angiography
- d. M-mode or 2D echocardiography

2. Blood Measures

a. Total cholesterol should be recorded on admission (if available) and obtained at the 4 month visit (optional)

3. 12-lead electrocardiogram

(obtained ≥ 3 days after qualifying MI and within 6 months of titration)

4. Battery of Baseline Forms

Dose Titration Measures

1. 24 hour Holter

- a. A 24 hour Holter should be obtained 4-10 (2-10 days for moricizine) days after the initiation of each drug and dose if the patient is free of intolerable adverse effects, including ECG effects noted on monitor or otherwise.
- b. A measurement of ECG intervals must be obtained for each drug and dose used.

Followup Measures

1. Routine Followup Visits are scheduled every 4 months.

a. Data to be collected at every visit include:

1. List of Medications
2. Adverse Symptoms
3. CAST Medication use

b. Additional data to be collected at 4 months and then annually include:

1. 12-lead ECG
2. Quality of Life form

2. Events - Certain events (presyncope, syncope, symptomatic unsustained or sustained (≥ 15 beats at ≥ 120 bpm) ventricular tachycardia, aborted death, adverse ECG effects including heart block, suspected proarrhythmia, worsened CHF, recurrent MI, angioplasty and cardiac surgery) will require specific data and may require additional followup and testing, e.g., 24 hour Holters and temporary or permanent discontinuation of CAST drug. These are referred to in detail in Section 9.

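### Section 6.G.1.a relaxes a QTc entry limit that Section 4.B does not contain: criterion 21 is congenital long QT syndrome, and no numbered exclusion bars an off-drug QTc of 0.6 s or more

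*Protocol*

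**What the plan says.** Section 6.G.1.a (Protocol) lists findings that end titration for good. One is any entry exclusion that appears during titration and is shown by washout not to be drug toxicity, with stated exceptions. The exceptions read "For this reason criteria 19, 21, and 22 are modified to" a QRS of 0.20 s or more, a QTc of 0.6 or more (no unit given there), and a pause of 3.5 s or more. The reason given is that some exclusions were there to head off safety problems on active drug, but that for a patient already in titration "there is no reason to exclude the patient unless the limit for concern is achieved".

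In Section 4.B, criterion 19 is a QRS of 0.18 s or more and criterion 22 a pause of 2.5 s or more. Criterion 21 is "Congenital long QT syndrome".

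Numerical QTc limits otherwise appear only for patients on study drug. Section 6.G.3.d uses 1.4 times baseline and/or 0.6 s during titration, and Section 9 item 5 uses the same limits in follow-up. Both places link marked QTc lengthening on antiarrhythmic drugs to sudden death.

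At the call that assigns the titration sequence, Section 7.A requires "assurance that no exclusionary criteria are present and that the informed consent was signed".

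**The concern.** A rule that modifies a criterion needs a criterion of the same kind to modify. Here a number is put in place of a diagnosis, with two consequences.

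- **During titration.** If criterion 21 now means a QTc of 0.6 or more, a patient whose congenital long QT syndrome is recognised in titration with a QTc below 0.6 no longer meets the stop rule as written.
- **At entry.** The stated reasoning presupposes that entry is stricter than the titration limit. For QTc there is no entry number at all, so a value that the protocol treats as its limit for concern is not screened for by any numbered exclusion.

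What is at stake is the safety of a small number of patients and a clean definition of who is eligible. Such a patient would take study drug before the first required on-drug recording: "A 24 hour Holter should be obtained 4-10 (2-10 days for moricizine) days after the initiation of each drug and dose". Under item 5 of the 1989 Protocol Revision the patient would first spend two weeks on blinded moricizine dose 1 or placebo, and so would also enter that randomised comparison.

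**Working it through.** There is no planned figure to reproduce and no power or alpha calculation applies. The check sets the texts side by side.

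**1. Entry limit against titration limit.**

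| Criterion | Entry, Section 4.B | Titration, Section 6.G.1.a | Difference |
|---|---|---|---|
| 19, QRS | 0.18 s | 0.20 s | 0.20 - 0.18 = 0.02 s looser |
| 21 | congenital long QT syndrome, no number | QTc 0.6 | not defined |
| 22, pause | 2.5 s | 3.5 s | 3.5 - 2.5 = 1.0 s looser |

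Two of the three are true relaxations. The third is not.

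**2. Is a QTc limit elsewhere in the list?** The exclusions run from 1 to 36 without a gap. The ECG items are 19 to 25: QRS width, WPW syndrome, congenital long QT syndrome, pause, AV block, sinus node dysfunction and slow heart rate. None gives a QTc value, and neither does any other item. A different criterion number in Section 6.G.1.a would therefore not repair the reference.

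**3. Does the 1989 Protocol Revision supply one?** Its exclusions (items 3a to 3c) concern ejection fraction, time from infarction to the qualifying Holter, and ventricular tachycardia. Item 9 redefines disqualifying ventricular tachycardia. None mentions QTc, and the introduction leaves everything not listed unchanged.

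**4. The same off-drug value at two times.** Take a patient whose QTc off drug is 0.6 s or more and who does not have the congenital syndrome.

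- Before titration: no numbered exclusion applies, so the assurance required by Section 7.A can be given truthfully.
- During titration, after washout: the modified criterion in Section 6.G.1.a is met and titration ends permanently.

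**5. Is the value available in time?** Yes. Section 6.B says: "Between the informed consent for titration and beginning titration, collection of the baseline data must be completed". Section 8.C adds: "A rhythm strip for interval measurements is to be made for each Holter and retained in the patient files". Section 4.A item 3 has the patient qualify off antiarrhythmic drugs. The reading needed for an entry rule already exists, and only the rule is absent from Section 4.B.

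**The case against.** The strongest reply is that this is a faulty cross-reference with little practical effect. Several parts of it stand.

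- **Other exclusions narrow the gap.** Hypokalaemia (14), digitalis toxicity (15), wide QRS (19), concurrent antiarrhythmic drugs (27) and recent amiodarone (28 to 30) remove some likely reasons for a long QTc, and congenital long QT syndrome remains an entry exclusion. Criterion 33, "Psychologically or physically unfit to participate in the study", lets an investigator decline the patient. That is judgement rather than a rule.
- **A sensible site would stop.** The interval can be read before the first dose, and a pre-drug value cannot be drug toxicity. This depends on the site acting beyond the numbered list.
- **Part of the protocol cannot be checked.** The contents page lists Sections 11.A-C, including one on starting therapy, and they are not in the available text.

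A reader might infer that nothing in the protocol stops such a patient from receiving drug. The documents do not support that, because Sections 11.A-C cannot be ruled out as a safeguard. What can be said is that no numbered exclusion does so.

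A reader might also infer that such patients would be moved needlessly from drug to drug. That needs the original multi-drug scheme, the optional washout of Section 6.H to be skipped, and the finding to be blamed on the drug, since Section 6.G.3 covers only effects shown to be due to it. In follow-up, Section 9 item 5 asks for washout verification. The 1989 revision leaves moricizine alone and allows only dose reduction in blinded retitration.

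Finally, the source of the error is not shown. It could be a wrong number, a QTc criterion lost from Section 4.B, or a deliberate new titration limit. All three leave the same inconsistency.

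**Conclusion.** The point holds as a minor safety and eligibility correction. Section 6.G.1.a modifies a QTc limit that the numbered exclusions do not contain. Taken literally, it displaces congenital long QT syndrome as a titration stop rule, and it leaves a non-congenital off-drug QTc of 0.6 s or more outside the numbered entry exclusions.

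The protocol gives no count of affected patients. That they are very few is a judgement, based on how extreme the value is and on the exclusions around it. No effect on power, alpha or the primary comparison is shown, and a reader should not infer one.

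The conclusion rests on the list in Section 4.B being complete as shown, which its unbroken numbering supports, and on no equivalent rule standing in Sections 11.A-C.

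**What to change.** 1. In Section 6.G.1.a, take 21 out of the modified list, so that congenital long QT syndrome stays in force unchanged during titration.
2. State a QTc of 0.6 s or more, with its unit, as a separate titration limit.
3. Add a numbered exclusion to Section 4.B, for example 37 so that no existing reference shifts: QTc of 0.6 s or more off antiarrhythmic drug, read from the rhythm strip of the qualifying Holter.

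The value 0.6 s is the minimum consistent choice, because it is the protocol's own limit. It does not create the margin that QRS and pause have: a patient at 0.59 s could still start. Whether to set a stricter entry value is a clinical decision for the investigators.

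The cost is amendment wording and one more item to confirm before the enrolment call. No new test is needed. The very few patients with such a baseline QTc would not be enrolled. If Sections 11.A-C already hold an equivalent rule, step 3 reduces to a cross-reference.
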